4.2.2 Hypothesis II

Caries progression may be imaged through a SFE laser optical device.

4.3 Previous Experience with the Study Material

4.3.1 Description of the clinical procedure

The proposed components of the infiltration kit are substantially equivalent to a variety of currently marketed dental materials in terms of physical and mechanical properties. The *indication for use* of the DMG “Infiltration kit for caries lesions” is micro-invasive treatment of early approximal caries. The materials will be used according to the label.

4.3.2 Preclinical Testing

The materials to be used for infiltration (etchant and infiltrant) have received EEC market authorization for medical devices [REDACTED]. Therefore, complete documentation of preclinical testing and biological evaluation of the device and its results has passed the appropriate regulatory bodies. Documentation and approvals are on file with the sponsor.

4.3.3 Previous Clinical Experience

The devices used in this study have seen clinical application for several years for infiltration indication with excellent results. The materials in the infiltration kit will be used according to label and for approved indication (micro-invasive treatment of early approximal caries). The materials have a low incidence of adverse events and no serious adverse events have become known.

The concept of caries infiltration applying the penetration of a low-viscosity resin into the porous lesion of enamel caries was proven on extracted teeth.^{25, 39} Furthermore, the positive effect on white spot depletion was shown on artificial lesions.²⁵ This in vitro study monitored the effect of Icon on

white spots over an eight week period. Icon had a significant effect on returning the subjected teeth to their natural color, whereas the fluoride toothpaste and gel applications did not.

4.3.4 Clinical Studies

Infiltrating a caries lesion is a currently introduced strategy to strengthen damaged tooth structure and to reduce caries progression without any surgical intervention.³⁹⁻⁴⁰ Management of early lesions by infiltrating instead of or postponing restorative treatment would have a great impact towards improving oral health care by means of its non-invasive nature. It will drastically lengthen the life-cycle of a tooth.²⁵ Infiltration would provide a simple and cost-effective management option with the least possible iatrogenic effect and diminished need for future re-treatment due to deteriorating of restoration margins.⁴¹

The promising in vitro results of caries infiltration on extracted teeth were underlined by different clinical trials. Several groups reported slower caries progression in infiltrated sites compared to controls: Radiographically obtained quantification reveals lesion progression in 16% of infiltrated sites compared to 53% for controls after one year and for 24% (infiltration group) and 62% (control) after two years. Recently, the three year follow-up data were published, reporting 32% progression for infiltrated lesion and 70% for controls in this split-mouth study.⁴² Meyer-Lueckel et al. measured progression rates of 7% (infiltrated sites) and 37% (controls) after 18 month in young adults.⁴³ The currently available 3-year data of this study report 4% progression in infiltrated lesion and 42% for controls.⁴⁴ Ekstrand et al. aimed to assess the efficacy of resin-infiltrated lesions covered by fluoride varnish (FV) versus FV treatment only of proximal lesions on deciduous molar teeth in a one year split-mouth study. Radiographically, 23% of the test lesions and 62% of the control lesions had progressed, comparable to the aforementioned results in young adults.⁴⁵

5 Device Risk Analysis and Assessment

5.1 Risk Analysis of the Medical Device

There is a minimal risk associated with the device itself and the procedures involved in its use, as identified by risk assessment and post-market experience of substantially equivalent materials, beyond the common risks related to standard dental treatment.

Definition: Minimal risk is the probability and magnitude of harm or discomfort anticipated in the research and not greater in and of themselves than those ordinarily encountered in daily life or during the performance of routine physical or psychological examinations or tests [45 CFR 46.102(i)]

The entire treatment in each aspect, including lesion size and location, all materials, equipment and techniques used, is part of regular daily life. Dentist visits, like in this study, resulting in caries detection, diagnosis and management by regular preventive regimen or sealant are not at all out of the ordinary. It is –alas- rather ubiquitous and a common part of daily oral health care provisions that our professions provides to the public. Therefore, the risk is NOT greater than routine dental practice. The care provided meets this definition of minimal risk.

The SFE technology has been used in multiple human applications safely and efficaciously. Therefore, there is low risk in use of the technology in the dental setting. The device was deemed to be a non-significant risk device by the FDA. If a child expresses dismay or stress during the SFE imaging process, the participant will be withdrawn from further study participation.

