6.1 Objectives

The main purpose of the present study is to evaluate the efficacy of a low viscosity resin (Infiltrant; DMG, Hamburg, Germany) in controlling the regression of White Spot lesions. As a secondary purpose, this study intends to evaluate the usage of SFE for investigation of penetration success and for visualization of early caries.

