6.2 Specific Aimes (Primary Endpoints)

6.2.1 Specific Aim I

- Caries arrest evaluated by bitewing radiographs

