6.3 Secondary Endpoints

- White spot reversal
- Secondary caries
- Post-operative sensitivity
- Color match / surface staining
- Surface quality / texture
- SFE for visualization of early caries and lesion depth assessment

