8.1 Baseline Records (*Radiography*)

Additional radiographs will not be taken for purpose of the trial only, they will be performed as part of standard of care. The policy described below reflects the widely accepted, current best practice regarding detection, diagnosis and monitoring of approximal lesions. Standardized diagnostic bitewing radiographs will be taken using an aiming device. The device facilitates optimal direction of the x-ray beam and thus leads to optimal diagnostic representation of the caries lesion.

Radiographic evaluation of the lesions and the quality of the adjacent enamel contact surface by standardized bitewing radiographs at baseline will be used to detect and diagnose the caries and monitor lesion change. An extensive review of the scientific evidence supports the importance of initial bitewings and radiographic recall examinations for description of caries progression.⁴⁹⁻⁵³ Both, the guidelines by Pitts and Kidd⁴ widely used in Europe, and the ADA/FDA-coordinated guidelines⁵⁴ advise that in high risk children (age 10-16) the interval should be 6-12 month. The proposed timing of bitewings in our study (baseline and at yearly intervals) falls well within these guidelines. They rather represent a minimum of the advised frequency for a caries-prone study population of adolescents and young adults in the age range of 6-13 years.

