8.2 Clinic visits

A trained study clinician will perform all standard clinical assessments of study lesions in groups 1 and 2, including visual exam and radiograph exam. The study clinician will provide Icon treatment to all study participants randomized to study arm 1 after the radiograph and visual exam. The study clinician will provide oral hygiene instruction and topical fluoridation therapy (Duraphat fluoride varnish) to all study participants randomized to study arm 2 after the radiograph and visual exam.

A trained study clinician will capture the SFE laser optical device image of the study lesions from all study participants. The study examiner will be trained and calibrated by the HPL research team prior to start of study. SFE laser optical device image diagnoses from baseline will be compared to diagnoses from radiograph and visual exams from chart review from the same visit.

Table 8.2 Overview of the procedures during each visit

Procedure	Screening visit	Baseline and Intervention	12 Month Follow-up	24 Month Follow-up
Time		D-0	M 12 (± 3 m)	M 24 (± 3 m)
Patient information	x			
Oral examination	x		x	x
Informed consent	x			
Medical history	x			
Inclusion and exclusion criteria	x		x	x
Selection of eligible lesions	x			
Caries risk assessment	x			
Placing ortho spacers(tx group) D-21 to -7 prior to BI		x	x	x
Randomization	x			
Radiographic examination		x	x	x
Examination by SFE Before spacers placed	(x)*	x		
Examination by SFE Before & After Icon placed		x	x	x
Examination by SFE		x		
Visual Assessment of lesion		x	x	x
Intervention (Infiltration) (EXPERIMENTAL)		x		
Instruction for oral health care		x	x	x
Record of adverse effects		x	x	x
Fluoridation (CONTROL)		x	x	x

*Can be done at screening or baseline appointment

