11.4 Statistical Analysis

11.4.1 Descriptive Statistics

Descriptive statistics (means, standard deviations, counts, and percentages) will be calculated for all variables. A Chi-square test of association will be performed to evaluate if there is a significant difference in caries arrest by treatment group at a significance level of 0.05. Additional Chi-square tests of association will be performed to determine if there is a significant association with the secondary outcomes by treatment group.

11.4.2 **Blinding**

Each subject enrolled into this study will be assigned a unique identifying code number. Every effort will be made to maintain the confidentiality of each study subject's identity. No presentation or publication of the study data will identify any study subject.

11.4.3 **Evaluation of Records**

SFE laser optical device image diagnoses from each time point will be compared to diagnoses from radiograph and visual exams from chart review from the same visit.

- For radiograph and visual exams: Assessments of caries lesions per standard of care will be abstracted from the electronic dental record system (Axium) and recorded on CRF.
- For SFE laser optical device image: Recordings from the device will be used to assess caries lesions and recorded on CRF.

11.4.4 **Missing Data**

Missing data due to dropouts have been accounted for in adjusted sample size. The missing data will be at random. Data of dropouts will be assigned as "last observation carried forward".

11.4.5 **Statistical Software**

STATA Data Analysis and Statistical Software will be utilized to perform data analysis.

12 Method of Reporting

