The primary endpoint in this study is the proportion of study lesions that have progressed, whereby a difference in caries progression of 40% after 2 years between resin infiltrated teeth and control will be assumed. This difference is based on a previous infiltration study by Ekstrand et al. [45] who reported a 1-year difference in caries progression in primary teeth of 39% (resin infiltration (23%) vs. control (62%)), which was furthermore comparable to results obtained in young adults. Martignon et al [42] for example reported a difference in caries progression in permanent teeth of 37% and 38% after 1 and 2 years respectively; and Meyer-Lueckel et al. of 30% after 18 months.

Based on an assumed difference in caries progression of 40% between resin infiltrated teeth and control, with alfa = 0.05 and a power of 80% the calculated sample size (t-test; matched pairs) would be 42 lesions to find significant differences. To allow for a potentially attrition rate of at least 20% over a period of 2 years a total of 50 lesions will be included.

Statistical Analysis

All evaluations are performed by one trained examiner. The primary outcome is proportion of study lesions that progressed after 2 years as measured via dental examination and pairwise comparison of radiographs. Differences between groups will be tested using Fisher's exact test.

Secondary outcomes are the proportion of study lesions that progressed after 1 year as well as change in categorical lesion depth (progression to next depth category lesion; E1->E2->D1->D2->filling) after 1 and 2 years as measured by pairwise comparison of radiographs. In addition, the change in categorical lesion depth will be determined via SFE laser optical device imaging after 1 and 2 years and compared to the change in categorical lesion depth as measured by pairwise comparison of radiographs. Differences in categorical lesion depth will be analyzed with Chi-square tests with 95% confidence interval (95% CI) and P = .05.

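### Distress during SFE imaging ends all study participation, so 2-year primary-outcome data that do not need SFE are lost avoidably

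*Combined protocol and SAP*

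**What the plan says.** Section 5.1 sets the rule: "If a child expresses dismay or stress during the SFE imaging process, the participant will be withdrawn from further study participation". It covers participation as a whole, and no section provides for outcome collection afterwards.

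The primary outcome is defined without SFE. SAP, Statistical Analysis: "The primary outcome is proportion of study lesions that progressed after 2 years as measured via dental examination and pairwise comparison of radiographs". Protocol section 6.2.1: "Caries arrest evaluated by bitewing radiographs". Section 8.1 says of the radiographs: "Additional radiographs will not be taken for purpose of the trial only, they will be performed as part of standard of care". Section 11.4.3 takes both the radiographic and the visual assessments from the electronic dental record.

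The status of SFE varies. Section 6.1: "As a secondary purpose, this study intends to evaluate the usage of SFE for investigation of penetration success and for visualization of early caries". Section 6.3 lists among the secondary endpoints "SFE for visualization of early caries and lesion depth assessment", and the SAP places SFE lesion depth with the secondary outcomes. Section 6.2, whose heading labels its aims as primary endpoints, makes agreement of SFE with clinical measures Specific Aim II.

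For missing data, section 11.4.4 declares them missing at random and says: "Data of dropouts will be assigned as" last observation carried forward (LOCF). Table 14.1.2 in section 14.2 names LOCF for some kinds of dropout but not for lost contact or withdrawn consent or participation. It has no row for SFE distress.

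**The concern.** Intolerance of one imaging procedure ends follow-up for an outcome measured by other means. Section 9.1 and Table 8.2 put randomization at enrolment, and SFE is then used at the intervention visit and at months 12 and 24, so these losses generally occur after randomization. They are also avoidable, because the bitewings are taken in routine care whether or not the child tolerates SFE.

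Two things are at stake in a 50-lesion trial: the number of lesions with an observed 2-year outcome, and how the unobserved ones are scored. Every eligible lesion is E1 or E2 at entry, so carrying a baseline value forward scores it as not progressed by construction. A missing-at-random assumption does not justify that score.

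**Working it through.** **Inputs.** From the SAP: 42 lesions required, 50 enrolled, attrition of at least 20% allowed for, Fisher's exact test, and progression rates of 23% (infiltration) and 62% (control) in the primary-teeth study behind the assumed effect. From section 9.3: 25 lesions per arm. From section 6.4: up to 2 lesions per child. The SFE distress rate is not given; 5%, 10% and 20% are assumptions. Power figures ignore clustering of lesions within children.

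**The plan's own figures.** A matched-pairs t-test with 0.40 read as a standardized effect, one-sided alpha 0.05 and 80% power gives 41 pairs, close to the stated 42. A two-sample t-test with an assumed SD of 0.45 gives 21 per arm, or 42. The step to 50 matches 42 × 1.2 = 50.4, whereas 42 / 0.8 = 52.5 would need 53. The reserve is therefore 50 − 42 = 8 lesions, or 8/50 = 16%.

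**Cost per child.** 1/50 = 2% or 2/50 = 4% of lesions. Eight lesions correspond to between 4 children (two lesions each) and 8 children (one each).

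**Lesions affected.** 50 × 0.05 = 2.5 and 50 × 0.10 = 5, so about 3-5. If these fall within the planned 20% attrition, nothing further is lost. If they come on top of it, 50 × 0.8 = 40 lesions become 40 × 0.95 = 38 or 40 × 0.90 = 36. Exact Fisher power at 23% versus 62% is 76% with 25 per arm, 60% with 20 and 59% with 18. The added loss of power at 10% distress is thus small.

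**If LOCF is applied and all distress occurs at baseline.** With a fraction *w* withdrawn equally in both arms, each observed rate becomes rate × (1 − *w*), with 25 lesions per arm still analysed:

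| *w* | Icon | Control | Difference | Fisher power |
|---|---|---|---|---|
| 0 | 23.0% | 62.0% | 39 points | 76% |
| 5% | 0.23 × 0.95 = 21.9% | 0.62 × 0.95 = 58.9% | 37 points | 71% |
| 10% | 0.23 × 0.90 = 20.7% | 0.62 × 0.90 = 55.8% | 35 points | 66% |
| 20% | 0.23 × 0.80 = 18.4% | 0.62 × 0.80 = 49.6% | 31 points | 55% |

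**Loss by visit.** Distress at baseline loses both follow-up readings. Distress at month 12 loses the 24-month reading, though the 12-month reading survives if the radiograph and visual exam come first. Distress at month 24 need lose nothing in that order, which is how section 9.5 lists the procedures without stating that the order is binding.

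**SFE exposure by arm.** A row of Table 8.2 reads "Examination by SFE Before & After Icon placed" and is marked at both follow-up visits, which suggests that follow-up SFE belongs to the Icon arm. Section 9.5 lists SFE imaging of study lesions at all follow-up visits with no arm restriction, section 8.2 has images captured from all participants, and section 11.4.3 compares SFE at each time point. The one clear difference is the additional exam after Icon placement in section 9.4.1.

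**The case against.** The rule is a cautious protection for children in a minimal-risk study, and the SAP already allows for attrition. At an assumed 5-10%, the 3-5 lesions fit within the reserve of 8. All of that is fair and limits the size of the point. It does not justify the loss, because SFE can stop for a distressed child exactly as it does now while routine records are still read.

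Several stronger readings are tempting, and the documents do not support them:

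- **Unequal loss between arms.** A reader might infer from Table 8.2 that the Icon arm has more SFE throughout. Only the post-placement exam clearly differs, and it follows a pre-placement SFE at the same visit that would already have tested tolerance. Losing 20% of Icon lesions and no controls would, under LOCF, create a spurious gap of 0.62 − 0.62 × 0.80 = 12 points in favour of Icon when both true rates are 62%, but nothing in the documents suggests such a split.
- **LOCF as certain.** Section 11.4.4 points that way. Table 14.1.2 is silent on this event and does not apply LOCF to every dropout.
- **The primary outcome always lost.** Distress at month 24 need not lose it.
- **SFE as plainly secondary.** Section 6.2 says otherwise. Neither status makes SFE necessary for the radiographic outcome.

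The consent form is not among the pages available, so it may already permit record abstraction after withdrawal.

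**Conclusion.** The point holds in limited form. As written, section 5.1 causes avoidable post-randomization loss of the primary outcome when distress occurs at baseline or month 12, at 1-2 of 50 lesions per child. The total is unknown because no distress rate is given, and it is probably modest: about 3-5 lesions if 5-10% are affected. If all of these were baseline withdrawals handled by LOCF, the 39-point difference would shrink to 37 or 35 points and power would fall from 76% to 71% or 66%. That is an upper case, since it assumes every withdrawal happens at baseline and that LOCF applies. A material difference between arms is not established. This is an inexpensive improvement that should be made, not a flaw that undermines the trial.

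**What to change.** Reword section 5.1 so that distress ends SFE imaging for that child and the SFE results are recorded as missing. The radiographic and visual or dental examination outcomes at 12 and 24 months should continue to be recorded from standard care unless the child or guardian withdraws. Both components are needed, because the SAP outcome uses the examination as well as the radiographs.

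Add a row for this event to Table 14.1.2, reconcile that table with section 11.4.4 on when LOCF applies, and check that the consent form allows the continued recording. Reconcile the Table 8.2 row label with section 9.5, and the status of SFE in section 6.2 with sections 6.1 and 6.3 and the SAP. Decisions on treatment and spacers for such a child remain with the investigator and are not addressed here.

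The cost is a sentence, a table row and, if needed, a consent line. The downside is that some lesions will have no SFE data, which is already so under the present rule.

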14.2 Withdrawal / Dropout of Subjects

Table 14.1.2 Withdrawal and drop-out of subjects separated by level, reason and consequences

Level	Cause	Consequence
Lesion	An allocated lesion progresses radiographically into the middle or inner 1/3 of dentin (criteria D2 and D3).	
The lesion is treated invasively by removing the caries and placing a filling.
 
The case is scored as "progressed" and "failure".

	The patient shows signs of reversible or irreversible pulpitis in an allocated tooth.	
The tooth is treated.
 
The case is scored as "progressed" and "failure".

Patient	The patient shows adverse reactions for one of the study materials.	
Counteractive measures are taken.
 
Unwanted effects are documented in CRF and CEF.
 
The patient is scored as "drop out", data will be assigned as "last observation carried

		forward".
	The patient can not be examined (i.e. x-ray during pregnancy)	The patient is scored as "drop out", data will be assigned as "last observation carried forward".
	One or more allocated lesions have been treated by an external dentist.	The patient is scored as "drop out", will be assigned as "last observation carried forward".
	The patient can not be contacted to make appointments.	The patient is scored as "drop out".
	The patient decides to withdraw his informed consent or study participation.	The patient is scored as "drop out".
Study	One or more patient(s) show severe unwanted side effects to treatment.	Individual counteractive measures are taken. The study is halted.
	More than five patients show unwanted side effects to one treatment or material used.	Individual counteractive measures are taken. The study is halted.

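### Carrying dropouts' last readings forward into the SFE–radiograph change comparison scores baseline-only lesions as agreement, and the plan has no rule that keeps imputed values out

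*Combined protocol and SAP*

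**What the plan says.** Four places bear on this point.

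- **Protocol 5.1 (risk analysis):** "If a child expresses dismay or stress during the SFE imaging process, the participant will be withdrawn from further study participation". Nothing is said there about how that child's data are handled.
- **Protocol 11.4.4 (missing data):** "The missing data will be at random", and "Data of dropouts will be assigned as 'last observation carried forward". No variable or endpoint is exempted.
- **Protocol 14.2, Table 14.1.2:** carry-forward is stated for three of the five patient-level causes: an adverse reaction, treatment by an outside dentist, and "The patient can not be examined (i.e. x-ray during pregnancy". For a patient who cannot be contacted, and for "The patient decides to withdraw his informed consent or study participation", the table says only that the patient is a dropout. Distress during SFE imaging is not listed. Lesions that reach the D2 or D3 category, and teeth with pulpitis, are handled differently: "The case is scored as 'progressed' and 'failure".
- **SAP, Statistical Analysis:** "the change in categorical lesion depth will be determined via SFE laser optical device imaging after 1 and 2 years" and set against the radiographic change over the same periods. The SAP has no missing-data rule. Its sample-size section adds lesions as follows: "To allow for a potentially attrition rate of at least 20% over a period of 2 years".

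Protocol 11.4.3 separately compares SFE diagnoses with radiographic and visual diagnoses from the same visit.

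**The concern.** A method-comparison analysis asks whether two instruments, each reading the same lesion, give the same answer. Carrying the last value forward breaks that when neither instrument was used at follow-up. The change from baseline becomes zero for both by construction, and the lesion enters the table as a concordant pair. Missing data are turned into evidence of agreement.

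One route to dropout is the SFE procedure itself, since a child distressed by the imaging is withdrawn. That fits poorly with the assertion in 11.4.4 that data will be missing at random. Up to two lesions per child are allowed, so one such withdrawal can remove two pairs.

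What is at stake is Specific Aim II (section 6.2.2), the correlation of SFE measurements with clinical measures, which the protocol lists under its primary endpoints. The treatment comparison (Specific Aim I) is not the subject here.

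**Working it through.** **What the rules do to one lesion.** Let the change at follow-up be the follow-up category minus the baseline category. The result depends on what was last observed.

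| Last readings available | SFE change used | Radiographic change used | Effect on the comparison |
|---|---|---|---|
| Baseline only, both methods | 0 (imputed) | 0 (imputed) | Counted as agreement |
| Follow-up film taken, SFE at baseline only | 0 (imputed) | observed | Agrees only if the film shows no change |
| Both methods at month 12, lost before month 24 | month-12 value | month-12 value | Month-12 agreement or disagreement repeated |
| No SFE image ever obtained | none | any | Nothing to carry forward; lesion drops out of the comparison |

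**Inputs.** 50 lesions and 20% attrition (SAP), so 0.20 × 50 = 10 lesions; the SAP's evaluable number of 42 would instead imply 50 − 42 = 8. The assumed share of lesions progressed on film is (23% + 62%)/2 = 42.5%, the mean of the two one-year rates the SAP quotes for primary teeth. The documents state no SFE–radiograph agreement and no SFE-distress rate, so there is no plan figure to reproduce. The SFE accuracies below are assumptions.

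**Upper-bound case: uninformative SFE, all 10 lesions baseline-only.** SFE readings are taken as independent of the film, with the same positive rate.

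- Agreement among observed pairs: 0.425² + 0.575² = 0.511; kappa 0.
- Expected table for 40 observed pairs: both progressed 40 × 0.425² = 7.225; each discordant cell 40 × 0.425 × 0.575 = 9.775; both unchanged 40 × 0.575² = 13.225.
- Adding the 10 imputed pairs, both unchanged becomes 23.225.
- Agreement: (7.225 + 23.225)/50 = 0.609.
- Progressed margin for each method: 17/50 = 0.34. Chance agreement: 0.34² + 0.66² = 0.551.
- Kappa: (0.609 − 0.551)/(1 − 0.551) = 0.13.

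**False positives.** In simulated trials (uncorrected chi-square test of SFE–film association at 0.05, SFE unrelated to film), the share significant was:

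| Baseline-only lesions imputed | 0 | 2 | 5 | 8 | 10 |
|---|---|---|---|---|---|
| Share significant | 5.3% | 5.6% | 7.7% | 11.6% | 14.8% |

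**Weakly informative SFE** (assumed sensitivity 60%, specificity 70%). The 40 observed pairs have 17 progressed and 23 not progressed on film, so the agreeing pairs number 0.6 × 17 + 0.7 × 23 = 10.2 + 16.1 = 26.3. Agreement is 26.3/40 = 66% and kappa 0.30.

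- *Both methods imputed for 10 lesions:* (26.3 + 10)/50 = 73%, kappa 0.39. With 2 lesions, kappa is 0.32.
- *Film observed, only SFE imputed for 10 lesions:* of these, 0.575 × 10 = 5.75 agree, so (26.3 + 5.75)/50 = 64%, kappa 0.25.

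For the uninformative SFE with only SFE imputed, kappa stays at 0 and the rejection rate stays at about 5%. The direction of the distortion therefore depends on which readings are missing.

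**The case against.** A reader might infer that every child withdrawn for SFE distress is counted as agreement, so that a failure of the device can never count against it. The documents do not support that. The first SFE examination falls at screening or baseline (Table 8.2), and distress there may leave no SFE value to carry. At follow-up, section 9.5 lists the radiograph ahead of SFE imaging, and films are standard of care (8.1). The list is not a mandated sequence, but a film without an SFE image is plausible, and agreement can then fall. Double imputation after SFE distress needs a usable baseline image followed by distress with no follow-up film.

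Nor can one say that all dropouts are carried forward as unchanged. Table 14.1.2 states carry-forward for three of five patient-level causes only, and a month-12 progression or disagreement would itself be carried to month 24. The table's silence does not cancel the general sentence in 11.4.4, however; it leaves the two sections in conflict.

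Three further points stand. The 10-lesion figures are a ceiling at the planned attrition, because the 20% covers all causes over two years. The same-visit comparison in 11.4.3 is not inflated this way: carrying values forward there only repeats earlier agreement or disagreement. And the standing of the SFE aim is mixed: 6.2 lists it as primary, 6.1 calls SFE a secondary purpose, 6.3 lists SFE depth assessment as secondary, and the SAP places the change comparison after its secondary outcomes. The plan does not name kappa or clearly specify a test of SFE–film association, so those measures are illustrations.

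None of this removes the core: nothing in either document keeps imputed values out of the change comparison.

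**Conclusion.** The concern holds in a limited form. Read together, section 11.4.4 and the SAP score any dropout with baseline readings only as concordant, without a follow-up image or film. Where only the SFE reading is missing, the same rule can lower agreement, so imputed values can distort the comparison in either direction.

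The size cannot be fixed from the documents. Under the stated assumptions it runs from negligible (2 baseline-only lesions: about 5.6% false positives against 5.3%) to material (10 lesions: about 15%, agreement 61% against 51%, kappa 0.13 against 0). Withdrawal for SFE distress is one source of such lesions, not the only one, and its handling is undefined. This should be corrected before analysis, but it does not bear on the treatment comparison.

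**What to change.** Add to the SAP:

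1. Last observation carried forward is not used for the SFE–radiograph comparison.
2. Only lesions with an SFE image and a radiograph both obtained at the same follow-up visit enter it.
3. Missing, stopped or ungradable SFE attempts are reported by arm, visit and reason.

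Reconcile protocol 5.1, 11.4.4 and Table 14.1.2 with the SAP, so that each cause of withdrawal, including SFE distress, has one stated data-handling rule. The rule for withdrawing a child need not change for this.

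A further analysis that counts stopped attempts as disagreement is optional.

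The cost is a few lines in the SAP and one field on the CRF. The downside is fewer pairs, about 40 instead of 50 at 20% attrition, and a wider interval. The pairs lost are ones in which at least one reading was never made.
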